Not opening the specimen through the tumour segment facilitates comparison of the cross sectional slices with MRI/CT imaging. The slices should be carefully inspected and the position of the tumour recorded according to the quadrants of involvement. The distance of direct spread outside the muscularis propria and the distance from the tumour to the nearest non-peritonealised margin should be recorded along with the tumour thickness. These measurements should be made initially from the slices and confirmed histologically e.g. by using the Vernier scale. Large blocks should be taken from the area closest to the circumferential margin wherever possible and also from any area where the tumour extends to within 3 mm of the non-peritonealised margin. Other blocks should be taken to allow at least 5 blocks of tumour to confirm presence or absence of extramural venous invasion. The number of any large blocks containing tumour can be subtracted from these 5. Likewise the peritoneal surface should be sampled by a minimum of 2 blocks if the tumour impinges on it (figure 3).

All of the local lymph nodes in the specimen should be identified, mapped, embedded and examined. The high tie (apical node) should be blocked separately to allow Dukes' staging to be conducted as should any lymph nodes marked (e.g. with a clip) by the surgeons to allow comparison with the intra-operative staging. The number of lymph nodes identified in each station (see below) should be noted on a diagram for subsequent mapping. If the nodes have not been marked by the surgeons, multiple nodes from the same station may be embedded in one block to cut down on the workload.

Figure 3: Suspected peritoneal/serosal involvement by tumour.

Histological reporting

We are using both Dukes' and TNM 5 for histopathological staging in this study, not TNM 6 or 7. This is because of the poor reproducibility of the TNM 6 definitions of extramural vascular invasion and lymph nodes. Thus we will be using the 3mm rule for nodal involvement, although these will be captured separately on the CRF. This allows the study to be consistent with other trials such as the Dutch TME trial and MRC CR07 trial. Dukes' staging allows easy communication between surgeons and the clinical team whereas TNM 5 gives more prognostic information, especially with respect to early tumours and local spread, e.g. peritoneal and direct spread (figure 3).

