		retroperitoneal and mesocolic resection margins
		on the cross-sectional slices
Intramesocolic plane	Moderate quality specimen	There may be moderate bulk to the mesocolon but significant irregularity of the peritoneal or fascial surface in at least one area that is deeper than five millimetres. The muscularis propria should not be visible. There may be moderate irregularity of the retroperitoneal and mesocolic
		resection margins on the cross-sectional slices
Muscularis	Poor quality	There may be little bulk to the mesocolon and
propria	specimen	there will be extensive defects that extend down

plane	to the muscularis propria. The retroperitoneal and
	mesocolic resection margins may be partially
	formed by the muscularis propria on the cross-
	sectional slices

Table 1: A detailed description of the pathological grading system used to describe the plane of dissection in colon cancer specimens.

Figure 6: Three fresh colon cancer specimens resected in the (A) mesocolic plane with an intact peritoneal window (arrow), (B) intramesocolic plane with a significant mesocolic defect (arrow), and (C) muscularis propria plane with a posterior perforation of the specimen (arrow).

Figure 7: Cross-sectional slices from three specimens resected in the (A) mesocolic plane, (B) intramesocolic plane with a significant mesocolic defect (arrow), and (C) muscularis propria plane with a defect extending down to the muscularis propria (arrow).

Mapping the lymph node stations

The specimen will be carefully dissected to map the location of all of the lymph nodes identified using the Japanese station sub-groupings (figure 8, table 2). The pathologist will mark on a specimen diagram and lymph node mapping table the number of nodes in each station and how many of these were fluorescent intra-operatively. An accurate block key will be kept so that it is clear which nodes belong to which station and whether or not they were fluorescent. The D1 nodes will be subdivided into those within 5cm of the tumour, those that lie between 5 and 10cm of the tumour and those that are more than 10cm beyond the tumour. Any non-fluorescent nodes in the same station may be embedded with more than one node in each block. Each fluorescent node will be blocked out individually. The apical node(s) will also be blocked separately to enable Dukes' staging.

As stated in TNM 5, extramural tumour deposits measuring ≥3 mm in maximum size are **Sponsor:** University of Leeds (GS11/9681)

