counted as involved lymph nodes even if no residual lymph node structure can be identified. Smaller deposits are regarded as apparent discontinuous extensions of the main tumour. The number of ≥3mm tumour deposits classified as lymph nodes should be indicated in the report. Any tumour deposits measuring >3mm (and therefore counted as lymph nodes under TNM 5) should also be mapped and blocked carefully.

The local pathologist will cut a single section from each lymph node block and report the number of positive and negative nodes in each station using conventional histopathology. A copy of the diagnostic glass H&E slides, pathology report, photographs, specimen sketches and lymph node blocks will then be sent to Leeds for central review. Deeper levels and immunohistochemical testing will be used on the lymph node blocks to confirm their status and detect missed metastases, micrometastases and isolated tumour cells. A final lymph node report will be issued identifying how many lymph nodes in each station were detected, how many were involved by tumour, and how this related to the intra-operative fluorescent nodes.

Figure 8: Japanese staging subgroups - Pericolic, D1 lymph nodes (red); Intermediate D2 **Sponsor:** University of Leeds (GS11/9681) lymph nodes (blue); Main, D3, lymph nodes (yellow).

Station	All nodes	Notes	Fluorescent	Cassette	Involved
number					
201	1	5-10cm	No	A1	No
	2	5-10cm	No	A1	No
	3	5-10cm	No	A1	No
	4	<5cm	Yes	A2	Yes
	5	<5cm	No	A3	No
	6	<5cm	No	A3	No
202	1		No	A4	No
	2		No	A4	No
	3		Yes	A5	No
203	1	Apical (ileocolic)	No	A6	No
	2		No	A7	No
	3		No	A7	No
	4		No	A7	No
211	1	>10cm	No	A8	No
	2	>10cm	No	A8	No
	3	5-10cm	No	A8	No
	4	5-10cm	No	A8	No
	5	<5cm	No	A9	No
	6	<5cm, deposit >3mm	No	A9	No
	7	<5cm	No	A9	No
212	1		No	A10	No

	2		No	A10	No
	3		No	A10	No
	4		No	A11	No
	5		No	A11	No
213	1	Apical (right colic)	No	A12	No
	2		No	A13	No
TOTAL	27 nodes		2 nodes		1 node

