Table 2: Example of how to map the lymph nodes for central review for a right hemicolectomy specimen including the station number, number of nodes in each station, whether the node was fluorescent, the cassette the node has been embedded in and whether or not it is involved. Note that comments have been provided to identify the apical nodes (there may be more than one apical node if the tumour lies between two vascular ties) and any nodes that are tumour deposits >3mm. Also the pericolic (D1) node are sub-classified into those >10cm from the tumour, 5-10cm from the tumour and <5cm from the tumour. The apical node(s) and any fluorescent nodes are embedded separately. All other nodes from the same station can be embedded in the same block, however, please do not embed more than four nodes in the same cassette.

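### Appendix 3: Table 2 breaks the protocol's own 3 mm rule for involved nodes, and histology is not stated to be read masked to fluorescence

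*Protocol*

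**What the plan says.** All of this is in the Protocol, mainly Appendix 3 (Histopathology proforma).

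**Deposits.** Under the TNM 5 rule, extramural deposits of at least 3 mm are "counted as involved lymph nodes even if no residual lymph node structure can be identified". The same paragraph then asks for deposits above 3 mm to be mapped and blocked, and the Table 2 caption also uses the strict inequality. In Table 2, station 211 node 6 carries the note "<5cm, deposit >3mm". It is marked No for fluorescent and No for involved, and the table totals one involved node.

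**Blocking.** "Each fluorescent node will be blocked out individually". By contrast: "Any non-fluorescent nodes in the same station may be embedded with more than one node in each block". Appendix 3 also says that, for nodes the surgeon has not marked, "multiple nodes from the same station may be embedded in one block to cut down on the workload". The Table 2 caption adds a ceiling: "please do not embed more than four nodes in the same cassette". Apical nodes are also blocked separately.

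**Reading.** "The local pathologist will cut a single section from each lymph node block". The pathologist records "the number of nodes in each station and how many of these were fluorescent intra-operatively", keeps a block key that includes fluorescence status, and is asked to keep the clips on fluorescent nodes visible in the photographs. The Table 2 caption describes the sheet as prepared for central review. Central review then uses deeper levels and immunohistochemistry on the lymph node blocks. Its final report states involvement and how involvement relates to fluorescence.

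**Use.** Section 8.1 and Section 17.1 rest both progression rules on comparison with histology. The second rule is assessed per patient. Section 8.1 also uses node-level information to help choose the dose.

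**The concern.** Histology defines both who enters the sensitivity denominator and which nodes count as missed by 5-ALA. Two things weaken it.

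First, the template shows pathologists an entry that the text forbids. If the entry is copied, a deposit that counts as an involved node is recorded as uninvolved. In the example the deposit is non-fluorescent, so the error deletes a missed node. A patient whose only involvement was such a deposit could be classed as node-negative and drop out of the analysis.

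Second, the reader of the reference standard can see the index result, and node handling depends partly on it. If a metastasis in a non-fluorescent node is overlooked, a false negative disappears and sensitivity rises. Each stage has only about ten node-positive patients, so one patient moved in or out can decide progression.

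**Working it through.** **1. Table 2 tally (inputs: its rows).** Nodes by station: 6 + 3 + 4 + 7 + 5 + 2 = 27. Fluorescent: station 201 node 4 and station 202 node 3, so 2. Marked involved: station 201 node 4, so 1. These reproduce the printed totals.

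Applying the 3 mm rule makes station 211 node 6 involved as well, giving 2 involved nodes.

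| Example, node level | As printed | Under the 3 mm rule |
|---|---|---|
| Sensitivity | 1/1 = 100% | 1/2 = 50% |
| Specificity | 25/26 = 96.2% | 24/25 = 96.0% |

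Per patient nothing changes: the patient is node-positive and detected through station 201 node 4 either way.

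The 2 fluorescent nodes occupy 2 cassettes. The 25 non-fluorescent nodes occupy 11, with up to 4 in one (A8).

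**2. The plan's own figure for the first rule.** Two-sided 99% Clopper-Pearson upper limit = 0.995 quantile of Beta(x + 1, n − x). For 1/10 it is 54.4% and for 2/10 it is 64.8%. The statement in Section 8.1 that at least 2 of 10 corresponds to an upper limit of at least 60% is reproduced.

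**3. The second rule (upper limit at least 80%).** With n = 10: 3/10 gives 73.5% (fail) and 4/10 gives 80.9% (pass). With n = 11: 4/11 gives 76.7% (fail) and 5/11 gives 83.1% (pass). One undetected node-positive patient left out of the count is therefore enough to turn a fail into a pass.

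**4. Illustrative size of bias from missed metastases.** The protocol gives no miss rates, so these are assumptions. Let S be true per-patient sensitivity, a the share of detected node-positive patients whom histology calls negative, and b the same share among undetected patients.

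Observed sensitivity = S(1 − a) / [S(1 − a) + (1 − S)(1 − b)]

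| S | a | b | Calculation | Observed |
|---|---|---|---|---|
| 60% | 0 | 10% | 0.60/(0.60 + 0.36) | 62.5% |
| 60% | 0 | 20% | 0.60/(0.60 + 0.32) | 65.2% |
| 70% | 0 | 10% | 0.70/(0.70 + 0.27) | 72.2% |
| 70% | 0 | 20% | 0.70/(0.70 + 0.24) | 74.5% |
| 60% | 10% | 10% | 0.54/(0.54 + 0.36) | 60.0% |
| 60% | 5% | 10% | 0.57/(0.57 + 0.36) | 61.3% |
| 60% | 10% | 20% | 0.54/(0.54 + 0.32) | 62.8% |

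Only the difference between a and b biases the result. Rows with a = 0 are an upper case for the chosen b.

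In that upper case (b = 10% to 20%), the binomial chance of at least 4/10 rises from 61.8% to 68.0–74.3% when S = 40%, and from 94.5% to 96.2–97.5% when S = 60%. The effect is largest for a weak test and small for a good one.

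**The case against.** A reader might infer that pooled blocking, unmasked reading and the Table 2 entry each hide metastases and inflate the sensitivity used for progression. The documents do not support that.

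- **Pooling.** One section through a block normally cuts every node in it, so a pooled node still gets one plane. A deficit arises only if the plane misses a node. Separate blocking has a stated purpose, comparison with the intra-operative staging, and apical nodes get it whatever their fluorescence.
- **Central review.** All lymph node blocks are sent, and deeper levels and immunohistochemistry have no stated restriction by fluorescence. This answers much of the sampling worry. What remains is that nothing requires each pooled node to be shown on the section.
- **Table 2.** It is a fill-in example. Appendix 3 also says 3 mm deposits are captured separately on the CRF and that their number is reported, so a copied No could be caught. The per-patient result in the example is unaffected.
- **Masking.** For the central reader, lack of masking is an inference: the sheet for central review carries the fluorescence column and no masking step is described, but the reading procedure is not set out. An analysis plan may also name the reference report.

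These points remove any claim of demonstrated inflation. They do not remove the contradiction in Table 2, or the case for masking a reading on which so few patients turn.

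**Conclusion.** Two points stand, of different weight.

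**Wrong as written:** the Table 2 row and total contradict the 3 mm rule, and the cut-off is stated two ways. The correct total under the protocol's rule is 2 involved nodes. This needs no assumption.

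**Worth improving:** central histology should be masked to fluorescence and named as the reference. The direction of bias from metastases missed in non-fluorescent nodes is upward, but at patient level only when every involved node in a patient is non-fluorescent and missed. Its size cannot be obtained from the documents. The figures of 62.5–65.2% (true 60%) and 72.2–74.5% (true 70%) are an illustrative upper case that assumes no misses in detected patients. The reason to act is how finely the second rule is balanced (4/10 against 4/11), not a proven distortion.

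**What to change.** 1. In Table 2, set station 211 node 6 to Yes for involved, change the total to 2 nodes, and use ≥3 mm in the text, the table and its caption.
2. Withhold the fluorescence column and block key from the central reader until the central involvement findings are locked. Add the comparison with fluorescence as a second step of the same report, since Appendix 3 requires that comparison.
3. At central review apply the same levels and immunohistochemistry to every node, and confirm that each node in a pooled block is on the section.
4. State that the locked central report is the reference for both progression rules.

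Individual blocking of clipped nodes can stay.

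The cost is a change of wording in Appendix 3, a separately held key, and perhaps a few recuts of blocks that already go to central review. Masking will be imperfect, because a single-node block hints at a fluorescent or apical node, and the local pathologist remains unmasked.

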Appendix 4: Surgical proforma

Introduction

The guidance below is provided with the aim of establishing a standard surgical procedure with regards to documentation of areas of fluorescence and extent of dissection and resection.

Operative assessment

The surgeon's details will be documented along with the patient's ASA.

The dosage and timing of administration of 5-ALA will be noted prior to initial laparoscopy, thus compiling a set of data to optimise the protocol during the evaluation phase. The settings of the Storz D-light laparoscopic system for 5-ALA fluorescence detection will also be documented.

The method of establishing pneumoperitonum and port site location and size will be performed according to the surgeon's preference.

Participants will undergo initial laparoscopic assessment to identify the overall lymphatic anatomy (colorimetric dye) and the presence of fluorescence (5-ALA) of lymph nodes, tumour and any additional areas within the parietal or visceral peritoneum.

Fluorescent lymph nodes will be marked with ligaclips to facilitate subsequent pathological identification.

The estimated location of the tumour and position of any fluorescent nodes (D1/D2/D3), including their size and number will be marked on the diagram (modified Japanese sub-group classification of nodal stations) in figure 1 and noted on table 1. The anatomy of the right colic artery will be noted on figure 2. Any anomalies involving a left sided resection will be noted on figure 3. Any additional areas of fluorescence; size, approximate location and whether excised as separate specimen will be noted on table 1.

Photos and videos will be taken via the laparoscopic stack to document areas of fluorescence.

Following initial laparoscopy patients will undergo segmental colectomy with D3 lymphadenectomy. A note will be made of the type of operation performed.

Right Hemicolectomy

For cancers of the right colon (caecum to the medial border of the falciform ligament) segmental colectomy with D3 lymphadenectomy will include:

- Incision of the mesocolon at the root of the ileocolic vessels, extending towards the planned site of terminal ileal division.
- Medial to lateral dissection in the retroperitoneal plane with ventral displacement of the right ureter and duodenum. Proximal dissection of the ileocolic vessels to their superior mesenteric origin.
- High, central ligation of ileocolic artery and vein
- High, central ligation of the right colic vessels, when present as separate branches
- Dissection of the middle colic vessels. For hepatic flexure cancers, the middle colic vessels will be taken at their origin. For caecal and ascending colon cancers, the right branch of the middle colic vessels will be taken at their origin
- Division of the terminal ileum
- Division of the lateral peritoneal attachments and mobilisation of the splenic flexure.
- Division of the transverse colon.
- Exteriorisation of the specimen through a wound of the surgeon's choosing
- Extracorporeal ileocolic anastomosis, by the surgeon's preferred method.
- Return to the bowel to the peritoneal cavity and closure of the wound using the surgeon's preferred technique.

Sigmoid Colectomy

For cancers of the sigmoid colon (distal to the level of the left iliac crest to 15 cm proximal to the anal verge) segmental colectomy with D3 lymphadenectomy will include:

- High ligation and division of the inferior mesenteric artery proximal to the origin of the left colic vessels.
- High ligation of the inferior mesenteric vein immediately below the inferior border of the pancreas
- Medial to lateral dissection with extension laterally under the left paracolic peritoneal

reflection, caudally over the sacral promontory to the mesorectal plane and superiorly to the transverse mesocolon

- Mobilisation of the splenic flexure where necessary
- Method of bowel division, specimen extraction and colorectal anastomosis will be as per surgeon's preference.

Operative procedure

The outcome of surgery, according to the opinion of the surgeon at time of operation, whether curative, palliative or unresectable will be noted. Any intra-operative complications, including excessive blood loss or open conversion will also be documented. Conversion to an open procedure will not affect the initial laparoscopic assessment and marking of fluorescent nodes; such patients will still be included in the trial. A note will be made of the duration of the operation, type of anastomosis, and extraction site of specimen.

Training video

Standardisation of operative procedure including D3 lymphadenectomy will be achieved through the production of a training video to standardise segmental right and sigmoid colectomy with D3 lymphadenectomy for the evaluation phase(4).

Figure 1. Modified Japanese staging subgroups - Pericolic, D1 lymph nodes (red); Intermediate D2 lymph nodes (blue); Main, D3, lymph nodes (yellow).

Station number 11	Vessel	Node	Estimate size of node (mm)	Comments e.g. Apical node	Colorimetric dyevisible Yes/No	Fluorescent Yes/no
21	D1 Ileocolic D2	2 1 2				
31	lleocolic D3	1 2		e.g.Apical (ileocolic)		
12	Right colic D1	1 2				
22	Right Colic D2	1 2				
32	Right Colic D3	1 2 3		e.g.Apical (right colic)		
13	Middle Colic D1	1 2				
23	Middle Colic D2	1 2				
33	Middle Colic D3	1 2		e.g.Apical node (middle colic)		

Station number	Vessel	Node	Estimate size of node (mm)	Comments e.g. Apical node	Colorimetric dyevisible Yes/No	Fluorescent Yes/no
41	Origin of SMA	1 2		Comment whether fluorescent (not excised)		
14	Left Colic D1	1				
24	Left Colic D2	1				
15	Sigmoid branche s D1	1 2				
25	Sigmoid Branche s D2	1 2				
16	Superior rectal D1	1				
26	IMA	1				
36	Origin of IMA	1		e.g.Apical node (IMA)		

Station number	Vessel	Node	Estimate size of node (mm)	Comments e.g. Apical node	Colorimetric dyevisible Yes/No	Fluorescent Yes/no
4	Any para- aortic nodes	1 2 3		Comment whether fluorescent (not excised)		
3 TOTAL	Any iliac nodes	1 2 3		Comment whether fluorescent (not excised)		
Additional Comments: Free text to add any additional areas of fluorescence – size, approximate location and whether excised as separate specimen.						

Table 1: Example of how to map the lymph nodes including the station number, vessel, number of nodes in each station, whether colorimetric dye was present, whether the node was fluorescent. Note that comments have been provided to identify the apical nodes (there may be more than one apical node if the tumour lies between two vascular ties). N.B. Right colic vessel may not be present - anatomy to be drawn in on Figure 2.

Figure 2. Right-sided resection. Modified Japanese staging subgroups.

To draw in vascular anatomy of right colic artery.

Figure 3. Left-sided resection.Modified Japanese staging subgroups.

To note any anomalies involving a left sided resection.

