Within the recruitment of the first 20 patients with positive lymph nodes, the ability of 5-ALA to detect positive nodes as compared to histology in at least 2 of 10 patients (in either cohort) will be required to progress to the next part of the study (see below). This corresponds to the upper bound of the 99% exact confidence interval of the sensitivity being at least 60% i.e. a good indication of activity given that the technical protocols and techniques may not yet be fully optimised. A 99% confidence interval has been chosen to reflect the additional uncertainty in 10 patients.

As the dose of 5-ALA is assessed, work will be carried out to standardise the preoperative radiological assessment, the technique of laparoscopic D3 lymphadenectomy and the pathological lymph node mapping.

If 5-ALA detects positive lymph nodes in at least 2 of 10 patients (in either cohort) then, from these initial results, the most promising dose of 5-ALA will be identified. Both patient and node-level information and practical considerations will be used to further inform this decision. At least a further 10 patients with lymph nodes with metastatic disease as judged by histological evaluation will then be recruited and treated with this schedule, with flexibility to include further patients to confirm the validity of the technique before proceeding to the evaluation phase. The exact number of patients will be determined in discussion with the TSC and DMEC prior to the start of this stage of the trial but, at their discretion, may be increased during this stage of the trial. We will aim to recruit up to 52 patients in total for the developmental phase. However, if necessary, more than this number of patients will be recruited to obtain this number with metastatic disease as judged by histological evaluation. The ability of 5-ALA FD to reliably detect lymph nodes with metastatic disease as judged by histopathological evaluation will be assessed by requiring that, to progress to the evaluation phase, the upper bound of the 99% (Clopper Pearson) confidence interval of the sensitivity (in the patients with positive nodes recruited in this stage of the trial) is at least the target value of 80%. This analysis will be versus histopathology but on a per patient basis, considering whether a patient has at least

1 node identified by 5-ALA. A 99% confidence interval has been used to reflect the additional uncertainty in a relatively low number of patients.

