11.2 Surgery: Segmental colectomy with D3 lymphadenectomy

Participants will undergo initial laparoscopic assessment to identify the overall lymphatic anatomy (colorimetric dye) and the presence of involved lymph nodes (5-ALA). Fluorescent lymph nodes will be marked with small surgical clips (e.g. Ligaclips) to facilitate subsequent pathological identification. Patients will undergo segmental colectomy with D3 lymphadenectomy. For cancers of the right colon, segmental colectomy with D3 lymphadenectomy will include central dissection at the origin of the ileocolic, right colic (when present) and middle colic vessels, with high vascular ligation and division. Specimen extraction and ileo-colic anastomosis will be as per surgeon's preference. For cancers of the sigmoid colon, segmental colectomy will include high ligation and division of the inferior mesenteric vessels proximal to the origin of the left colic vessels. Specimen extraction and colo-rectal anastomosis will be as per surgeon's preference.

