11.3 Histological assessment of lymph node status

The sites of any fluorescent nodes will be marked at operation using small surgical clips. Photographs of the fresh specimen with the clips in place with a cm scale will be taken in theatre to assist the pathologists. Resection specimens will be subjected to in depth histopathology, as per the Royal College of Pathologists guidance. See appendix 3 for further details.

Additional assessment will include:

- i) specimen photography and assessment of the completeness of mesocolic resection
- ii) distance of tumour and bowel wall to vascular ligation and length of vessels
- iii) area of lymphadenectomy
- iv) level of lymphadenectomy based on vascular anatomy
- v) histological analysis and mapping of lymph nodes identified by colorimetric

dye/5-ALA for metastatic deposits.

vi) Assessment of whether it is possible to visualise the fluorescent nodes at the time of cut up to further assist localisation of at the time of microscopy by fluorescent illumination.

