15.2 Secondary Endpoints

- Standardisation of preoperative CT reporting, with emphasis on lymph node evaluation
- Standardisation of operative procedure including D3 lymphadenectomy
- Optimisation and standardisation of fluorescence detection system.
- Standardisation of pathological lymph node mapping and step sectioning for in depth lymph node evaluation.
- Patient factors affecting the accuracy of 5-ALA fluorescence diagnosis.
- Safety

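### Section 11.2 and Appendix 4 contradict each other on the middle colic vessels in caecal and ascending colon cancers, so the nodal field sent to reference histology is not fixed

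*Protocol*

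**What the plan says.** Section 11.2 sets the operation for cancers of the right colon without dividing them by site. It requires "central dissection at the origin of the ileocolic, right colic (when present) and middle colic vessels, with high vascular ligation and division".

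Appendix 4 covers the same operation in more detail. Its stated aim is "establishing a standard surgical procedure with regards to documentation of areas of fluorescence and extent of dissection and resection", and it counts as right colon everything from the caecum to the medial edge of the falciform ligament. After a step that dissects the middle colic vessels, it separates the sites. One instruction, "For hepatic flexure cancers, the middle colic vessels will be taken at their origin", matches Section 11.2. The other sets a different extent at the two remaining sites: "For caecal and ascending colon cancers, the right branch of the middle colic vessels will be taken at their origin".

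The reference standard is histology of what is removed (Section 11.3): "Resection specimens will be subjected to in depth histopathology, as per the Royal College of Pathologists guidance". Section 8.1 says of the final progression criterion: "This analysis will be versus histopathology but on a per patient basis". Section 8.1, item v, lists standardising the colectomy and D3 technique between the two centres among the parameters to be optimised, and Section 15.2 lists "Standardisation of operative procedure including D3 lymphadenectomy" as a secondary endpoint.

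**The concern.** In this trial the surgical instruction also helps to define the reference standard. Fluorescence is read and nodes are clipped at the initial laparoscopy, before resection, but only nodes in the specimen get histology. If the text leaves open whether the root of the middle colic vessels is taken, a fluorescent or metastatic node there may be verified in one patient and stay unverified in another with the same tumour site.

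That bears first on the node-level results, which Section 8.1 uses, with patient-level results and practical considerations, to choose the dose. It can also bear on who counts as node-positive, and so on the denominator of the per-patient sensitivity. Finally, the findings and the training video are meant to carry a standard operation into the evaluation phase, and a protocol that describes two operations for one site does not supply that standard.

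**Working it through.** **1. The texts side by side**

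| Tumour site | Section 11.2 | Appendix 4 | Agree? |
|---|---|---|---|
| Hepatic flexure | Middle colic vessels at origin, high ligation and division | Middle colic vessels taken at origin | Yes |
| Caecum, ascending colon | Middle colic vessels at origin, high ligation and division | Right branch only, taken at its origin | No |

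Dividing a trunk at its origin and dividing one branch at its origin are different instructions. Neither section refers to the other on this point or gives an order of precedence.

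**2. Whether other parts of the protocol settle it**

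They do not.

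- Table 1 of Appendix 4 has a row for middle colic D3 (station 33). It lacks the remark that the nodes are not excised, which stations 41, 4 and 3 carry.
- The worked right hemicolectomy table in Appendix 3 shows ileocolic and right colic apical nodes and no middle colic one, but it is only an example.
- The operative CRF list in Section 13.4 asks for the type of operation, not for the vessels divided or the level.

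**3. How sensitive the progression criteria are to one patient**

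The contradiction itself contains no figure to recompute. For context, the two-sided 99% Clopper-Pearson upper bound for x detected of n node-positive patients is the 0.995 quantile of Beta(x + 1, n − x).

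- First-stage rule, at least 2 of 10 for an upper bound of at least 60%: 2/10 gives 64.8% and 1/10 gives 54.4%. The protocol's statement is reproduced.
- Later rule, upper bound at least 80%: 4/10 gives 80.9% (met), 3/10 gives 73.5% (not met) and 4/11 gives 76.7% (not met).

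At this boundary, one undetected patient added to the node-positive group (4/10 to 4/11), or one detection lost among ten (4/10 to 3/10), reverses the decision. Ten is the minimum for this stage; the actual number is left to discussion with the TSC and DMEC.

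**4. When the contradiction could produce such a change**

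Only when a patient's node-positive status, or detection by 5-ALA, rests solely on nodes in the disputed field. The protocol gives no rate for this, so its probability cannot be computed.

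**The case against.** The strongest reply is that Appendix 4 merely details Section 11.2: the middle colic vessels are dissected in all right-sided cases, and the appendix then says by site what is taken. That is a possible reading, and it narrows the conflict. It does not remove it, because Section 11.2 attaches high ligation and division to every vessel it names.

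Other points on that side stand:

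- Some variation in the field is intended. Appendix 4 varies it by tumour site, and sigmoid resections have a different field altogether.
- The extent actually achieved is largely recoverable. Section 11.3 records the area and level of lymphadenectomy, the distances to the vascular ligation and the vessel lengths. Appendix 3 has the vascular ties measured and all nodes mapped by station. Variation could therefore be described afterwards, although that does not tell the surgeon which operation to perform.
- Standardisation is an output of this phase, the analysis is descriptive, and the final criterion excludes patients treated before the schedule was chosen.
- Each initial cohort is filled until it has 10 node-positive patients, so there a patient whose status changed would be replaced rather than lost.

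A reader might infer that the two centres examine different nodal fields. Nothing in the protocol shows that the surgeons follow different sections; the text only fails to rule it out.

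**Conclusion.** The contradiction is real and confined to caecal and ascending colon cancers. It leaves the extent of resection, and with it the nodal field submitted to histology, open to the surgeon's choice of section. It is worth correcting because both texts are operative instructions, they help define the reference standard, and a uniform operation is one of the trial's stated products. No effect on the dose decision or on either progression criterion is demonstrated.

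Three figures invite a stronger conclusion that the protocol does not support.

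- The 6% in Section 6.4 concerns spread along the right branch of the middle colic artery in caecal cancers. Both descriptions remove that branch, so the figure does not measure the disputed tissue.
- The segmental shares in Section 6.1 give 25/(25 + 20) = 56% right-sided among eligible sites. That includes hepatic flexure tumours, where the texts agree; the caecal and ascending share is not given.
- It might seem that one patient in ten moves sensitivity by 10 points. That holds for a change in detection among a fixed ten. A change in node status alters the denominator: from 4/10 = 40.0% to 4/11 = 36.4%, 4/9 = 44.4% or 3/9 = 33.3%, a shift of about 4 to 7 points.

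**What to change.** The sponsor and the surgeons should reconcile Section 11.2 and Appendix 4 into one description by tumour site, or state in one place which text governs. Appendix 2 already records caecum, ascending colon, hepatic flexure and sigmoid as separate locations, so a description by site needs no new classification. Which extent of resection is right is a surgical matter on which this review takes no view.

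Optionally, the operative CRF could record which vessels were divided and at what level. That would complement the pathology record of lymphadenectomy level and let the node-level analysis show which patients had station 33 within the examined field.

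The cost is a wording change and, if adopted, one CRF item. The sample size, the visits and the progression criteria stay as they are.
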